8.1. Inclusion Criteria

Subjects must meet all inclusion criteria to be enrolled in this study:

1. Willing to provide signed informed consent
2. Adults age 21 to 80
3. Fitzpatrick Skin Type (FST) I to VI
4. Presence of benign pigmented Lesions assessed at baseline as Pigment Severity Score (PSS) of "2" or higher and/or wrinkles assessed at baseline as Fitzpatrick Wrinkle Score (FWS) of "2" or higher
5. Willing to allow photographs and/or video to be taken of treated areas for the purposes of this research study
6. Willing to abstain from any other procedures for treatment of benign pigmented lesions or wrinkles in the laser treatment areas for the duration of the study including surgery, light, laser, ultrasound or radiofrequency treatments
7. Willing to abstain from use of prescription cosmetic products for treatment of benign pigmented lesions or wrinkles in the laser treatment areas for the duration of the study including injections of neurotoxins or dermal fillers, skin lightening creams, and wrinkle creams
8. Willingness to adhere to study treatment and follow-up visit schedules

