	
 10. Severe immunosuppression resulting from medications and/or a medical condition that could impair healing after treatment. 11. Open wound or infection in the intended treatment area 12. History of light induced seizure disorders 13. Dermatologic and/or cosmetic procedures in the intended treatment area(s) during the past six months 14. The subject is not suitable, in the opinion of the clinician, for participation in the study due to medical or other reasons that could compromise the study integrity or subject safety
Study Visit Outline	
NOTE: Screening Visit and Baseline/Treatment Visit #1 may occur on the same day
 
Screening Visit:
 
 1. Informed Consent 2. Inclusion and Exclusion Criteria Review 3. Medical History Review 4. Concomitant Medication Review 5. Fitzpatrick Skin Type (FST) Evaluation 6. Benign Pigmented Lesion and Wrinkle Evaluation 
Baseline / Treatment Visit #1:
 
 1. Clinical Photography 2. Laser Treatment 3. Local Skin Response Assessment 4. Subject Pain Score Assessment 5. Safety Assessment 6. Skin Biopsy (optional) 
Telephone Contact
 
 1. 10 days +/- 7 days after each treatment 
Treatment Visits #2 to #4:
 
 1. Clinical Photography 2. Subject Satisfaction Score 3. Laser Treatment 4. Local Skin Response Assessment 5. Subject Pain Score Assessment 6. Safety Assessment 7. Skin Biopsy (optional) 
Follow-Up Visits: 4 ± 1 week, 8 ± 2 weeks, 12 ± 4 weeks.
 
 1. Clinical Photography 2. Subject Satisfaction Score 3. Local Skin Response Assessment 4. Safety Assessment 5. Skin Biopsy (optional)
Measurement Instruments	
5-Point Pigment Clearance Scale (Appendix A)
 
9-Point Fitzpatrick Wrinkle Scale (Appendix B)

	
11-Point Subject Pain Scale (Appendix C)
 
5-Point Subject Satisfaction Scale (Appendix D)
 
Local Skin Response (Appendix E)

Primary Efficacy Endpoints	
1. Benign Pigmented Lesions Mean difference from Baseline to 12-week follow-up in Pigment Clearance Score (PCS) as determined by blinded evaluators from clinical photography
 
2. Wrinkles Mean difference from Baseline to 12-week follow-Up in Fitzpatrick Wrinkle Score (FWS) as determined by blinded evaluators from clinical photography

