9.1. Pigment Clearance Score (PCS)

Clearance of pigment following study treatment will be measured using a validated 5-point Pigment Clearance Scale (PCS) that categorizes improvement in the appearance of pigmented lesions from 0=0% or No Improvement to 4=75-100% or Excellent Improvement.¹⁴ The PCS scoring scale is provided in Appendix A.

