10.1. Screening Visit

The following activities typically take place during the Screening Visit.

Informed Consent

The site will provide detailed information about the study, including study procedures, visit schedule, potential risks and benefits and alternative treatment options. The subject will be given time to review the informed consent form (ICF). If the subject wishes to participate, he/she will complete the ICF with a signature and date. The original will be retained with subject's study records and a copy will be provided to the subject.

Medical History

Subject's medical history, including dermatological treatment history and assessment of medication use will be documented.

Pregnancy Test

Women of childbearing potential will undergo a urine pregnancy test. Subjects with a positive pregnancy test are ineligible for study participation.

A woman of childbearing potential is defined as a premenopausal female capable of becoming pregnant. This includes women on oral, injectable, or mechanical contraception; women who are single; women whose partners have been vasectomized or whose partners are utilizing mechanical contraceptive devices.

Treatment Area Examination and Lesion Identification

Wrinkle evaluation will be performed using the Fitzpatrick Wrinkle Score. Benign pigmented lesions, a description of lesion type anatomical location, and size will be documented.

Inclusion/Exclusion Criteria Review

Study inclusion and exclusion criteria will be reviewed to verify study eligibility.

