17.1. Primary Effectiveness Endpoints

Benign Pigmented Lesions

Mean difference from Baseline to final 12-Week follow-up visit in Pigment Clearance Score as determined by blinded evaluators from clinical photographs.

Wrinkles

Mean difference from Baseline to final 12-Week follow-up in Fitzpatrick Wrinkle Score as determined by blinded evaluators from clinical photographs.

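### The primary pigment endpoint subtracts a Baseline Pigment Clearance Score that does not exist, and the severity score that gates Group A entry is neither graded nor recorded in the documents

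*Combined protocol and SAP*

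**What the plan says.** **Entry.** Section 8.1, criterion 4 (repeated in the synopsis), requires for the pigment indication: "Presence of benign pigmented Lesions assessed at baseline as Pigment Severity Score (PSS) of" 2 or higher. The score (PSS) appears elsewhere only in the abbreviation list.

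**Screening.** Section 10.1 says of pigment: "Benign pigmented lesions, a description of lesion type anatomical location, and size will be documented". The synopsis lists a general item at the same visit: "Benign Pigmented Lesion and Wrinkle Evaluation".

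**Scale.** Section 9.1 says: "Clearance of pigment following study treatment will be measured using a validated 5-point Pigment Clearance Scale (PCS". Appendix A gives the grades as bands of percent clearance. Section 18 has three blinded evaluators look at Baseline and post-treatment photographs in pairs, pick out the Baseline one, and rate the improvement they see.

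**Endpoint and analysis.** Section 17.1 defines the primary pigment endpoint as: "Mean difference from Baseline to final 12-Week follow-up visit in Pigment Clearance Score". Section 19.2 instead states the Group A hypothesis as a proportion with good to excellent improvement. Section 19.3 powers that proportion at 50% against 75% with 30 evaluable subjects. Section 19.4 describes a paired t-test, from baseline to study exit, for a skin pigmentation score.

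**The concern.** There are two linked gaps on the pigment side.

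First, a numerical entry threshold rests on a score whose range, direction and anchors are not given, and no procedure records a value for it. Section 26 treats enrolment outside the criteria as a reportable major deviation. Section 19.1 has the biostatistician classify deviations before database lock, and section 19.4 removes major ones from the Per Protocol efficacy set. For the pigment part of criterion 4, that classification would have neither a definition nor a specified data item to work from.

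Second, and more serious, the primary pigment endpoint asks for a subtraction with one term missing. A clearance rating is already a comparison with Baseline, so there is no separate Baseline PCS to subtract. An analyst following section 17.1 would have to invent one, and the natural choice, the lowest grade, decides the sign of the result in advance.

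**Working it through.** **1. Is PSS defined or collected anywhere in the documents?**

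- Synopsis instrument list: the pigment entry is "5-Point Pigment Clearance Scale (Appendix A"), which is the PCS. PSS is not listed.
- Section 9: PCS, wrinkle scale, pain and satisfaction. No PSS.
- Section 10.1: a description of the pigmented lesion, without a severity score.
- Section 10.2: photographs before each treatment, but no pigment score.
- Table 1: no PSS row. This carries little weight alone, because the table names neither the PCS nor the wrinkle score.
- Appendices A to E: five instruments, none of them PSS.

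Section 9 and all five appendices are present and unredacted, so removed text does not explain the absence of grades.

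**2. Can PCS serve as the entry score?** No. In Appendix A a score of 2 means 25 to 49% clearance, which has no meaning for a lesion not yet treated.

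**3. Can the section 17.1 endpoint be computed?** Write P for a subject's 12-week PCS and B for the Baseline PCS. The endpoint is the mean of D = P − B.

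- P comes from the paired reading in section 18.
- B has no source. The Baseline photograph is the reference for P and is not graded separately.

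Suppose B is set to the lowest grade m. Section 9.1 runs from 0 to 4, so m = 0. Appendix A runs from 1 to 5, so m = 1. Under either coding P ≥ m, so D ≥ 0 for every subject, and the mean of D is zero only if every subject receives the lowest grade. A lesion that darkened could score no lower than one that did not change. Because B is then a constant, a paired t-test reduces to a one-sample test of whether mean PCS exceeds the floor of its own scale. Reading noise can move that mean in one direction only.

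**4. Does the gap reach the Group A sample size?** Inputs from section 19.3: n = 30, null rate 0.50, alternative 0.75, two-sided exact binomial test, 5% Type I error.

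- The rejection limit is the smallest r with 2 × P(X ≥ r | 30, 0.50) ≤ 0.05.
- r = 20: 2 × 0.0494 = 0.0987, too large.
- r = 21: 2 × 0.0214 = 0.0428, accepted. This is 21/30 = 70%.
- Power: P(X ≥ 21 | 30, 0.75) = 0.803, against the stated 80%.

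The plan's figure reproduces. None of its inputs involves PSS or a Baseline PCS.

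**The case against.** The strongest reply is that this is loose wording. Criterion 4 says the lesions are assessed at baseline, the synopsis lists a pigmented-lesion evaluation at Screening, and section 10.1 describes only what typically happens. An assessment is therefore implied. The case report forms are not among the documents, and Figure 1 (allocation logic) is not shown. This stands in part. The documents do not show that PSS will go unscored. They show that no grades are supplied and no procedure names or records it. Taken alone, that is close to a missing detail.

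On the endpoint, one can say that mean PCS at 12 weeks is computable and is what the sponsor meant. That may be so, but it is not what section 17.1 states, and the paired test in section 19.4 needs two values per subject. Section 19.4 attaches facial wrinkle sites to the pigment score, so its two tests may be interchanged. If so, the exact binomial test belongs to pigment, which supports the fix below. Having evaluators identify the Baseline photograph does not supply a worsening grade either, since no rule scores a wrong pick.

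Four stronger readings are tempting, and the documents do not support them:

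- **A spurious difference of a fixed size under no effect.** Its size would depend on an assumed Baseline that no section proposes, and on which of the two PCS codings is used.
- **Very faint lesions will enter and inflate percent clearance.** No figure or passage shows this, and section 7 also leaves enrolment to the investigator's judgement of eligibility.
- **The wrinkle arm is sound where pigment is not.** Section 18 applies the same paired improvement reading to both scales, and the Screening wrinkle score is not part of that blinded reading.
- **Blinded evaluators must grade severity on single photographs.** That would create a new endpoint. It is a design preference, not a correction the plan needs.

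**Conclusion.** The point holds in two parts. The primary pigment endpoint as worded cannot be computed, because PCS has no Baseline value and no grade for worsening. A Baseline placed at the scale minimum would make the mean difference non-negative by construction under either coding. Separately, the pigment part of inclusion 4 cannot be applied uniformly or verified from what the documents specify.

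The reach is the eligibility check for all Group A subjects (30 evaluable planned) and the primary pigment endpoint with any paired test of it. The responder hypothesis, its n = 30 and its power of 0.803 are unaffected, because they use neither PSS nor a Baseline PCS.

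The conclusion assumes that the sections shown are the complete description of the pigment instruments, and that neither Figure 1 nor the unseen case report forms contain the PSS grades. If they do, the eligibility part reduces to a missing cross-reference. The endpoint part would remain.

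**What to change.** 1. In section 17.1 and the synopsis, remove the subtraction of a Baseline PCS. Define the primary pigment endpoint as the blinded paired PCS clearance rating at 12 weeks, analysed as the responder proportion of sections 19.2 and 19.3 with the exact binomial test. Name the response categories that count, because section 9.1 and Appendix A number them differently. Align section 19.4. Mean PCS at 12 weeks can still be reported, described as a mean rating and not as a change. This needs no extra subjects or readings.

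2. For inclusion 4, do one of two things. Either supply the PSS grades as an appendix and record the score at Screening, in section 10.1 and Table 1, before allocation to Group A; or remove the PSS cut-off from the criterion. The choice is the sponsor's.

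The cost is wording changes plus, if PSS is kept, one appendix and one case report form field.

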8.2. Exclusion Criteria

Subjects who meet any exclusion criteria cannot be enrolled in the study:

1. Pregnant, planning pregnancy or breast feeding
2. Allergy to topical or injectable lidocaine or similar medications
3. Allergy to topical steroid or similar medications
4. Unprotected sun exposure in the six weeks prior to enrollment, or active tan in the laser treatment area
5. History of melanoma in the intended treatment area
6. History of keloid or hypertrophic scar formation
7. Use of topical or systemic retinoid therapy during the past six (6) months
8. Use of neurotoxins in the intended treatment area within the past three (3) months or throughout the duration of the study
9. Use of dermal fillers in the intended treatment area within the last six (6) months or throughout the duration of the study
10. Severe immunosuppression resulting from medications and/or a medical condition that could impair healing after treatment.
11. Open wound or infection in the intended treatment area
12. History of light induced seizure disorders

13. Dermatologic and/or cosmetic procedures in the intended treatment areas during the past six months that would compromise study integrity
14. The subject is not suitable, in the opinion of the clinician, for participation in the study due to medical or other reasons that could compromise the study integrity or subject safety

9. Measurement Instruments

9.1. Pigment Clearance Score (PCS)

Clearance of pigment following study treatment will be measured using a validated 5-point Pigment Clearance Scale (PCS) that categorizes improvement in the appearance of pigmented lesions from 0=0% or No Improvement to 4=75-100% or Excellent Improvement.¹⁴ The PCS scoring scale is provided in Appendix A.

9.2. Fitzpatrick Wrinkle Scale (FWS)

Improvement in the appearance of facial wrinkles following study treatment will be measured using the validated 9-point Fitzpatrick Wrinkle Scale (FWS) that categorized wrinkle severity from 1=Fine Wrinkles to 9=Deep Wrinkles.¹⁵ The FWS scoring scale is provided in Appendix B.

9.3. Subject Pain Scale

Immediately after each treatment subjects will be asked to rate the amount of pain experienced during treatment using an 11-point Subject Pain Scale ranging from 0=No Pain to 10=Extreme Pain. The Subject Pain Scale is provided in Appendix C.

9.4. Subject Satisfaction Survey

At each study visit beyond Treatment Visit #1 the subjects will be asked to rate their level of satisfaction with the treatment results so far using a 5-point Subject Satisfaction Survey ranging from -2=Extremely Dissatisfied to 2=Extremely Satisfied. The Satisfaction Survey is provided in Appendix D.

10. Study Visit Procedures

10.1. Screening Visit

The following activities typically take place during the Screening Visit.

Informed Consent

The site will provide detailed information about the study, including study procedures, visit schedule, potential risks and benefits and alternative treatment options. The subject will be given time to review the informed consent form (ICF). If the subject wishes to participate, he/she will complete the ICF with a signature and date. The original will be retained with subject's study records and a copy will be provided to the subject.

Medical History

Subject's medical history, including dermatological treatment history and assessment of medication use will be documented.

Pregnancy Test

Women of childbearing potential will undergo a urine pregnancy test. Subjects with a positive pregnancy test are ineligible for study participation.

A woman of childbearing potential is defined as a premenopausal female capable of becoming pregnant. This includes women on oral, injectable, or mechanical contraception; women who are single; women whose partners have been vasectomized or whose partners are utilizing mechanical contraceptive devices.

Treatment Area Examination and Lesion Identification

Wrinkle evaluation will be performed using the Fitzpatrick Wrinkle Score. Benign pigmented lesions, a description of lesion type anatomical location, and size will be documented.

Inclusion/Exclusion Criteria Review

Study inclusion and exclusion criteria will be reviewed to verify study eligibility.

10.2. Baseline and Treatment Visits

The following activities typically take place during each Treatment Visit.

Pregnancy Test

Women of childbearing potential will undergo a urine pregnancy test. Subjects with a positive pregnancy test will be discontinued from the study. The subject will be followed until the outcome of pregnancy is determined.

Photography

Prior to each laser treatment the treatment areas will be photographed using a high-resolution digital camera. Camera settings and other parameters such as distance, lighting, background and polarization will be recorded and reproduced at subsequent photography sessions.

Subject Satisfaction

At each treatment visit beyond Treatment #1, subjects will be asked to rate their level of satisfaction with the study treatments thus far using the Subject Satisfaction Scale provided in Appendix D.

Eye Safety

The correct eye protection must be worn during all laser treatments by the subject, the treating Investigator, and all other study personnel or observers in the room during laser operation.

Treatment Area Preparation

The intended treatment area will be cleansed with isopropyl alcohol or similar prior to treatment to ensure the treatment area is free of any makeup, creams or lotions.

Skin Biopsy (Optional)

Subjects may be asked if they will allow one or more skin punch biopsies to be performed at or near the treatment area prior to and/or immediately after treatment. Biopsies are optional and will only be performed after written consent is obtained from the subject. The Investigator will determine if biopsies are needed based on the condition being treated, location, or other factors. Performance of the biopsy typically follows these steps:

- a) Skin biopsies will be collected at or near the treatment area.
- b) Biopsy site will be cleansed with isopropanol alcohol or similar.
- c) Local anesthetic injection (lidocaine or similar medication) will be administered intradermally to the biopsy site prior to collection.
- d) Biopsy will be collected using sterile, single use disposable 2 mm to 4 mm punch biopsy.
- e) Sutures may be used to close the biopsy site as needed.
- f) Biopsies will be placed in a container labeled with Subject's ID number and date of collection.
- g) Biopsies will be fixed and processed for hematoxylin and eosin staining and/or scanning electron microscopy according to laboratory guidelines.

Anesthesia

To reduce pain and discomfort during laser treatment, the Investigator may recommend use of a topical anesthetic product, such as EMLA or LMX-4 cream, which is applied to the intended treatment area for approximately 60 minutes prior to treatment. The Investigator may also recommend use of a local intradermal injection of anesthesia, such as lidocaine or similar medication. Nonmedicinal methods may also be offered such as simple ice packs, or devices that provide cold air, such as a Zimmer cooling device (Cryo 6, Zimmer Medizin Systems, Irvine, CA). Subjects may also elect to be treated without anesthesia.

Test Spots

Test spots may be performed prior to treatment to help the Investigator establish appropriate treatment parameters to achieve the desired clinical endpoint such as erythema or whitening. Test spot parameters will be guided by subject skin type, lesion type, color or location among other factors. The procedure for test spots involves delivering a laser pulse to the skin at or near the treatment area using a low energy, fluence or other setting, and then increasing the relevant parameters until the desired clinical endpoint is achieved. For the PicoWay® laser system the clinical endpoint is most commonly erythema or whitening of the skin.

Laser Treatment

Study laser treatments will be administered using treatment parameters recommended by the manufacturer and study Sponsor, Candela Corporation. The treatment location, wavelength, handpiece, pulse energy, number of passes, and number of pulses will be documented in the case report form.

Benign pigmented lesions including dyschromia will typically be treated with either the 532 nm or 1064 nm Resolve™ Fusion, or 730 nm handpiece.

Wrinkles including fine lines will typically be treated with the 1064 nm Resolve™ Fusion handpiece.

The investigator will determine the treatment specific parameters including wavelength, energy, fluence, spot size and repetition rate for each subject based on the type, color and location of the lesion among other factors. For darker skin types FST V and FST VI the 1064 nm wavelength is most commonly used.

Pain Assessment

Immediately after each treatment subjects will be asked to rate the amount of pain experienced during treatment using an 11-point Subject Pain Scale ranging from 0 (No Pain) to 10 (Extreme Pain). The Subject Pain Scale is provided in Appendix C.

Local Skin Response Assessment

Local skin responses will be assessed and recorded following each laser treatment, normally within the first 30 minutes. The Local Skin Response Form is provided in Appendix E and includes the following most commonly observed skin responses which are both anticipated and in some instances desired clinical endpoints:

- Erythema
- Edema
- Whitening
- Petechiae
- Pinpoint Bleeding
- Purpura
- Crusting
- Blistering
- Burning

Safety Assessment

Local skin responses occurring from prior laser treatments that are deemed more serious due will be recorded as Adverse Device Effects (ADE) on the appropriate study case report form. Examples of anticipated ADE that can be observed following treatment with the PicoWay™ laser include:

- Hyperpigmentation
- Hypopigmentation
- Scarring
- Infection
- Herpes Simplex Activation

Although highly uncommon in conjunction with PicoWay® laser treatments, any Unanticipated Adverse Device Effects (UADE) will also be recorded on case report forms and reported to the Sponsor and IRB as required.

Post-Treatment Care Instruction

Subjects will receive instructions on post-treatment care of their treated areas. These may include the application of a petrolatum gel (such as Aquaphor® or Vaseline®); use of a topical corticosteroid (such as Cortizone®); avoiding sun exposure or use of tanning equipment; and use of a sunscreen with sun protection factor (SPF) 30 or greater for the duration of study.

Telephone Contacts

The Study Doctor or staff will make up to three (3) attempts to contact subjects by telephone 10 days after each treatment (+/- 7 Days) to assess healing response.

